 - i. The research coordinator will check the participant's medical record to make sure they have had their viral load tested within the previous 3 months. If not, their entry in the study will be delayed until after they have obtained viral load testing.
 - ii. The research coordinator will inform the participant that they have been placed in the Intervention group.
 - iii. The coordinator will schedule the participant's first videoconferencing session (1 ½-2 hours) with the study interventionist using the shared calendar, where they will receive their smartphone (if needed) and breathalyzer
 - iv. The research coordinator will provide the participant with a copy of the Participant Manual, which includes instructions for downloading the breathalyzer app on to their own phone, if they choose to use it.
 - v. The coordinator will encourage the participant to try downloading the app, and tell them that the interventionist will be in touch soon and can help them to install the app if need be
 - b. If they are in the waitlist-control group (Group 2):
 - i. The research coordinator will check the participant's medical record to make sure they have had their viral load tested within the previous 1 month (within 3 months of the intervention starting), or has plans to get it tested within the following 2 months. If not, their entry in the study will be delayed until after they have obtained viral load testing.
 - ii. The research coordinator will inform the participant that they have been placed in the waitlist-control group
 - iii. The participant will be provided the chance to complete the baseline assessment at that time on a laptop computer. If they choose not to complete it, the interventionist will call them to provide introductions and give them the web address for completing the questionnaire. This web address will also be provided to the participant on a handout.
6. The research coordinator will ask the participant the following questions about their cell phone:
 - a. Do you prefer to use a study phone or your own phone? (Study Phone/Own Phone)
 - b. If they prefer to use their own phone:
 - i. Do you own a smartphone? (Y/N)
 1. If no, inform participant that they must use a study phone, which will be provided at their first appointment
 - ii. What type of phone is it? (Android/iPhone/Windows/Other)

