 - c. Have you ever had to cancel or shut off your cell phone service for a period of time because the cost of maintaining the service was too expensive? (Y/N)
 - i. If yes, how recently did this occur? (More than a year ago/Less than a year ago)
 1. If less than a year, inform participant that they must use a study phone, which will be provided at their first appointment
 - d. Do poor or dropped signals prevent you from using your cell phone? (Y/N)
 - i. If yes, inform the participant that they may need to use a study phone. The interventionist will contact them before their first appointment to determine if one is needed.
 - e. How often do you reach the maximum amount of data you are allowed to use as part of your cell phone plan? (Frequently/Occasionally/Rarely/Never)
 - i. If "frequently" or "occasionally," inform the participant that they must use a study phone, which will be provided at their first appointment.
 - f. If responses indicate that they can use their own phone: Ask the participant to view the instructions for downloading the BACTrack app in the Participant Manual and ask them to download it to their phone before coming in for the initial meeting.
7. After the research coordinator asks these questions they will also ask the participant to provide information on their best emergency contact. The participant will be notified that this emergency

contact will only be called if necessary and that all information regarding their involvement in the study will be kept confidential.

- a. If it is an emergency and a patient cannot be reached, study staff will reach out to the emergency contact
8. The research coordinator will then notify the study interventionist through email of the newly-recruited patient by providing the Study ID number only.
9. The interventionist will be notified of a patient's initial appointment time through the shared calendar.
10. One day before the videoconferencing session, the interventionist will contact the participant to remind them of their appointment.

Step 3: Intervention Delivery

3a. Intervention group

1. One day before the videoconferencing session, the interventionist will contact the participant to remind them of their appointment.
 - a. If they are using their own phone and were not able to download the app before the last contact point, check in regarding the app installation at this point

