8. During Session 8, the interventionist will schedule the following appointments, contacting the patient one day before all subsequent tasks to remind them:
 - a. Post-intervention appointment at the VA to complete assessment and return equipment (1 week later)
 - b. Booster session (to be completed via phone 5 weeks later)
 - c. Questionnaire #3, to be completed 9 weeks later
 - d. Questionnaire #4, to be completed 17 weeks later
9. The final session at the VA (Week 8) will include the following tasks:

- a. Returning of mobile phones (if applicable) and breathalyzers
- b. Post-intervention assessment battery, completed using a laptop
- c. Reminder of all subsequent appointments/tasks for the study
10. At 12 weeks, the interventionist will contact the participants to complete a 30-minute intervention booster session via phone. This session will review the participant's drinking goals and provide a refresher on the different types of triggers and strategies to address them.
11. At 16 weeks, the interventionist will contact the participants and ask them to complete a follow-up assessment battery at home (on a computer, tablet, or mobile phone—no clinic visit will be required)
 - a. Participants will be given the option to come to the VA to complete the questionnaire if desired
 - b. If assessment is not done within a week, researchers will contact the participant to encourage participation and ensure that no adverse events had occurred
 - i. If patients cannot be reached, researchers will attempt to contact them three additional times (one day later, three days later, and one week later). If they cannot be contacted by the third attempt, they will be considered lost to follow-up and will not be contacted again.
12. At 24 weeks, the interventionist will contact the participants and ask them to complete an additional follow-up assessment battery at home (on a computer, tablet, or mobile phone)—no clinic visit will be required
 - a. Participants will be given the option to come to the VA to complete the questionnaire if desired
 - b. If assessment is not done within a week, researchers will contact the participant to encourage participation and ensure that no adverse events had occurred

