- Alcohol and drug use
- Alcohol-related beliefs
- Mental health status (anxiety, depression, stress, history of mental health diagnoses)
- Coping processes
- Emotion regulation
- Coping self-efficacy
- Quality of life
- Perceived social support
- Perceived HIV stigma
- HIV diagnosis date and transmission source
- Technology use
- Technology attitudes
- Health literacy
- Demographic information
- COVID-19-related history, protective behaviors, attitudes, and beliefs
- Knowledge of intervention materials (follow-up only)

Confidential online questionnaires and correspondence, completed on mobile phones twice daily, concerning the following variables:

- Alcohol intake, via survey response
- Medication use, via survey response
- Engagement in COVID-10 protective behaviors and COVID-19 related stress, via survey response
- Blood alcohol content, via breathalyzer reading sent to study coordinator
- Anxiety and depression, via survey response

Confidential online questionnaires, completed on tablets or mobile phones immediately following each of the 8 intervention sessions and concerning the following variables:

- Ratings of session experiences
- Attitudes toward session
- Perceived therapeutic alliance
- Open-ended reaction to the session

Retrospective chart review of viral load based on blood draws conducted as part of routine clinical care.

Data Storage

All survey and questionnaire data will be collected using Qualtrics survey software, which encrypts data and utilizes password-protected accounts. The "Anonymize Responses" option will be selected to avoid collection of IP addresses. Participants will only be asked to include their numeric study ID as part of their survey response, and will not need to provide any other identifying information. Any downloaded data will be kept on password-protected computers. Once data collection is completed and data files have been downloaded to a local computer, the data on Qualtrics will be deleted. The Qualtrics surveys will be housed

on the University of Georgia's Qualtrics account, which is used by the study interventionist and coordinator. The funder PI, [name], is at the University of Kentucky and will have shared access to the de-identified datasets.

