For questionnaires completed in the clinic, the tablets will be pre-loaded with links to the online surveys. For surveys conducted via mobile phone, participants will be texted a link to the assessments, which they can then open and complete using a mobile browser. At the beginning of the survey, participants will enter a unique identifier assigned to them at enrollment, which they can ask the interventionist for at any time in case they forget. Any data files containing contact information and identifiers will be kept separate from the survey responses on a secure, password-protected computer. Following the completion data collection, identifying information will be permanently removed from all electronic files. Participants will be trained regarding how to secure their mobile phone using a password, and the mobile phone used by the counselor will also be secured.

The interviews following the open trial will be conducted only by researchers affiliated with the project and not by individuals working at the VA. Responses will be recorded digitally. Recordings will then be transcribed by a research assistant and any identifying information will be removed, with pseudonyms used if necessary. Following the transcription of all files, which will be kept on password-protected computers, the recordings of the interviews will be deleted. The transcripts will be stored with all other research data and kept for 6 years before being destroyed.

The twice-daily self-monitoring completed by participants involves breathalyzer readings collected via text message. Each phone will be pre-loaded with contact information for the study coordinator's dedicated cell phone to reduce any chances of confusion or sending the information to the wrong individual. Both the participants' and coordinator's phones will be secured using a password, and coordinators will manually upload readings to a computer using a USB cable. After they are uploaded, the coordinator will delete readings from their phone. Study phones will likely be used by multiple participants throughout the rolling enrollment procedure of the intervention, so each phone will undergo a factory reset to avoid compromising any previous participants' data. This will not be necessary if participants choose to use their own phones for the study.

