To protect against loss of confidentiality, we will follow strict data management procedures. Access to data will be permitted only to the researchers and counselors, who will be trained in HIPAA procedures and will sign confidentiality agreements. Any contact information will be stored separately from responses and permanently deleted following the completion of data collection. Consent and HIPAA Authorization forms, which will be the only physical forms with identifying information, will be kept in a locked file cabinet in the coordinator's office. Moreover, members of the research team (e.g., research assistants) will be required to participate in training in the areas of ethics, confidentiality protection, and human subject participants. They will also be trained on a protocol regarding how to avoid identifying research participants who are seen out of the research setting.

To secure data on mobile phones, respondents will be taught how to delete messages or photos if they are worried about their information being compromised. Both respondents and counselors will be trained regarding and required to secure their phone using a password. A web-based service that allows complete control over data will be chosen to deliver the self-monitoring reminders, and any data collected during this process will be downloaded to a secure computer and deleted from the website following the completion of data collection. Finally, all phones will be capable of being remotely wiped in the case of loss or theft to protect participants' information. After each participant concludes with the intervention, the phone will undergo a factory reset to remove any traces of data or identifying information. Together, these steps are more than adequate to minimize and protect against risk.

6. Potential benefits/risks

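### The counselor who delivers TRAC is not separated from the outcome batteries and session ratings, which leaves an unmanaged risk of courtesy responding

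*Combined protocol and SAP*

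**What the plan says.** **Who delivers TRAC.** Under Step 2 (Patient Enrollment), item 5a, "The coordinator will schedule the participant's first videoconferencing session (1 ½-2 hours) with the study interventionist using the shared calendar". Step 3a, item 10 adds: "At 12 weeks, the interventionist will contact the participants to complete a 30-minute intervention booster session via phone". Interventionist and counselor are therefore the same role.

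**Where the answers sit.** Data Storage puts all survey and questionnaire data in Qualtrics, on a "Qualtrics account, which is used by the study interventionist and coordinator". Each response carries the numeric study ID. The anonymising option is chosen to suppress IP addresses; it does not remove the ID.

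**Who can link an answer to a person.** The coordinator emails the interventionist about each "newly-recruited patient by providing the Study ID number only" (Step 2, item 8). The Data security Plan describes the participant's identifier as one "which they can ask the interventionist for at any time in case they forget", and also states: "Access to data will be permitted only to the researchers and counselors".

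**What is collected there.** The batteries at baseline and weeks 8, 16 and 24 include alcohol and drug use. The survey after each session covers session experience, session attitudes and "Perceived therapeutic alliance".

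**Who asks for follow-up.** For the intervention arm, Step 3a, item 11 says: "At 16 weeks, the interventionist will contact the participants and ask them to complete a follow-up assessment battery at home". Item 12 gives the interventionist the same task at week 24. For the waitlist arm at week 24, Step 3b, item 15 assigns it to researchers, without further detail.

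**The concern.** A participant who thinks the counselor may read the answers has a reason to report less drinking, better adherence and a better session. If that reason is stronger in one arm, the difference goes into the treatment comparison, and a larger sample does not remove it.

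Two outputs are at stake. Acceptability is part of the first research question, and the SAP summarises it with an averaged session-attitude score that has no comparator. The SAP also says the aim of the week-8 comparison is effect sizes as preliminary evidence of efficacy, because the study is not powered for significance. A directional shift in Cohen's d would bear on that output.

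**Working it through.** The plan gives no figure for this point, so there is none to reproduce. The check has two parts.

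**1. Tracing exposure by analysis**

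- *Session-attitude score.* Five adjective-pair items about the session are averaged. If courtesy raises every item by the same amount, the mean rises by that amount. This is arithmetic only and says nothing about how large the amount is. Therapeutic alliance, the item nearest to a rating of the counselor, is collected but not named in the SAP.
- *Week-8 comparison between arms.* The treated arm completes the battery at the VA after Session 8 (Step 3a, items 8 and 9). The waitlist arm completes it on arrival, before its first session (Step 3b, items 6 to 9), after an introductory call and contacts at weeks 4 and 7. Daily monitoring, including the breathalyzer, runs only in each participant's own 8-week intervention period (section 5, Collection and record keeping). The waitlist arm therefore has no readings in weeks 0 to 8, and the alcohol comparison rests on self-report. The same is assumed for adherence: the list of battery variables does not name it, but the SAP compares it between arms.
- *Pooled change from baseline.* There is no control arm here, so any shift that arises after baseline enters the estimate directly. The interventionist's follow-up requests can matter only here. For the intervention arm the SAP names T2 and T3, so the week-16 battery enters; its week-24 battery is not among the named time points.

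**2. Scale of a possible shift at week 8**

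Inputs: N = 50 (section 3). The allocation ratio is not stated, so 25 per arm is an assumption. The significance level is 5% (SAP), taken as two-sided. The differential reporting shift b is assumed to be 0.1 to 0.3 SD, and the true effect is set to zero.

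SE(d) ≈ √(1/n₁ + 1/n₂) = √(2/25) = √0.08 = 0.283. The 95% half-width is 1.96 × 0.283 = 0.55.

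| Assumed shift b (SD) | Added to d | b / 0.283 | Chance of p < 0.05 (t test, 48 df) |
|---|---|---|---|
| 0.1 | 0.1 | 35% | about 6% |
| 0.2 | 0.2 | 71% | about 11% |
| 0.3 | 0.3 | 106% | 18% |

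The last column uses a noncentral t distribution with noncentrality b/0.283; with no shift it would be 5%. The result depends little on the split: with 20 and 30, SE(d) = √(1/20 + 1/30) = 0.289, and the range becomes 35% to 104%.

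If a fraction f of the shift comes from believing that the counselor can see the answers, the fix removes f × b. The documents give neither f nor b. With b up to 0.3 and f anywhere from 0 to 1, the removable part lies between 0 and 0.3 in d.

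**The case against.** Several stronger readings are tempting, and the documents do not support them.

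- *The counselor reads the answers and the results are biased.* Shared use of an account and general permission to access data do not show that individual answers are opened. The questionnaires are self-completed and labelled confidential. What participants are told about visibility would be in the consent form or the Participant Manual, which are not in the available text, so the lack of such a statement cannot be called a proven gap.
- *The interventionist's follow-up requests inflate the week-8 effect size.* They come at weeks 16 and 24, after that comparison. At week 8 the interventionist only schedules and reminds; no one is named as asking for the battery.
- *The whole 0.1 to 0.3 SD is avoidable.* Allocation is open, and the counselor discusses recent drinking reports in sessions by design (section 4, Study Intervention). Some under-reporting could persist whoever held the account.
- *The acceptability score rates the counselor.* Its items rate the session, and alliance is not named in the SAP.

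It is also fair to doubt that moving contact to the VA coordinator would improve candor. That person screens medical records and refers high AUDIT scores to the clinical team, and the protocol keeps VA staff out of its open-trial interviews.

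All of this stands, and it limits the claim. It does not supply a separation between the counselor and the answers, and it does not change the unequal contact by arm at week 8.

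**Conclusion.** The point holds as an unmanaged risk of courtesy responding, not as a demonstrated bias. The account use, data permission and ID knowledge are documented, and no available section keeps the interventionist from the batteries or session ratings. The exposed outputs are the session-attitude score, the self-reported week-8 comparison of alcohol use and adherence, and the pooled change-from-baseline analysis.

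The size is unknown. The range of 35% to 106% of SE(d) rests on two assumptions, 25 per arm and a differential shift of 0.1 to 0.3 SD. At the low end the effect is slight: the chance of a false significant result goes from 5% to about 6%. Only the part due to perceived counselor visibility is preventable. In an unpowered pilot this is a cheap improvement and does not call for redesign.

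**What to change.** 1. In Data Storage and the Data security Plan, set survey-level permissions so that the interventionist cannot view the post-session surveys or the baseline, 8-, 16- and 24-week batteries until that participant's last assessment. Keep the daily monitoring surveys visible, because sessions use them.
2. State on each restricted survey that the counselor will not see the answers.
3. Where feasible, have existing study staff who do not deliver TRAC send the battery links and handle ID look-ups, with the same requester in both arms. This step is optional; the first two do not depend on it.
4. In the SAP, note as a limitation that the week-8 alcohol comparison has no breathalyzer data for the waitlist arm.

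**Cost.** A permission change, one sentence per restricted survey and, if step 3 is taken, some contact tasks moved to other staff. No new staff, visits or sample size are needed. The counselor loses real-time use of session ratings. Social desirability in an open-label trial is reduced, not removed.

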- Does participation in the TRAC intervention lead to improvements in medication adherence?

- Does participation in the TRAC intervention impact other clinical HIV outcomes, including CD4 count and viral load?

3. Study Objectives

The aim of the study is to conduct a pilot randomized controlled trial of the TRAC intervention among PLWHA:

- Two-month, randomized-controlled waitlist trial with 2-month follow-up ($N=50$)
- Feasibility evaluation, focusing on recruitment, engagement, and adherence
- Evaluation of effects on overall alcohol consumption, HAART adherence, and clinical outcomes

4. Study Design

Description of relevance to the VA

HIV occurs among veterans at a higher rate than among those in the general population. Moreover, many veterans struggle with alcohol use disorders, which can impact their health and overall quality of life. The TRAC intervention, which aims to reduce alcohol use among people living with HIV/AIDS, thus meets two important needs among the VA patient population.

Study Population and patient selection

Subject Inclusion Criteria: To be eligible to participate in the intervention, patients must be 1) HIV-positive, 2) 18 years and older, 3) an at-risk drinker as identified through a screening procedure, 4) currently taking HIV medication and 5) a patient receiving care at one of the study recruitment sites. Based on NIAAA's screening recommendations, every person living with HIV who reports to participating clinics will complete a short screening procedure. Clinical data of interest including alcohol dependency diagnoses and prescription use will be pulled from CDW via VINCI, CCR and HAVACS. These clinical indicators will be used to create a list of eligible patients with appointments in the coming month for screening. The list of eligible patients will be stored in the secure VINCI project folder and then downloaded to the secure local VA drive for use by study coordinators. The only two locations in which the list will be stored are within VINCI and on the secure local drive. After a list of patients has been created, the study coordinator will screen the patient EMR (CPRS/VISTA) for inclusion criteria.

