Patients who are identified as eligible will be screened using a survey if they are interested in participating. First, they will be asked if they sometimes drink alcoholic beverages. If yes, they will be asked how many times in the past month they have had 5 or more drinks in a day (for men) or 4 or more drinks in a day (for women). They will also be asked if, on any week in the past month, they have had more than 14 drinks (for men) or more than 7 drinks (for women). If they answer yes to either of those questions, they are considered to be an at-risk drinker and will qualify for the study. This screening may also be conducted over the phone if the participant indicates interest in the study but is unable to complete the screening procedure while visiting the clinic. If the screening procedure indicates that the participant is eligible, they may begin the study within 30 days time.

Subject Exclusion Criteria: Individuals who are HIV-negative, less than 18 years of age, who are not identified as an at-risk drinker through the alcohol screener, or who are not currently prescribed HIV medication will not be eligible to participate. For the randomized controlled trial, participants who have not had their viral load tested within the 3 months prior to beginning the intervention (3 months before baseline for the Intervention group, 3 months before the 8-week time point for the Waitlist-Control group) will not be eligible to begin the study until they have had bloodwork completed. Additionally, participants will take the AUDIT questionnaire as part of the study screener. If they score a 20 or higher, indicating alcohol dependence, they will not be eligible for study participation.

Study Recruitment

After screening, patients who are deemed eligible for the study may be recruited in the following ways:

- An IRB approved letter mailed to the patient and then after two weeks the patient may be contacted over the phone or in person at a clinic visit about the study unless they decline
- Through an approved study flyer or direct patient initiated contact to the study coordinator
- A clinic provider refers patient to study or gives patient study flyer at clinic visit

- Direct patient contact in the clinic at clinic visit
- Outreach to a patient who has previously signed an informed consent form for another research study which allowed for future contact

Study Intervention/Investigational Product

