 - i. If patients cannot be reached, researchers will attempt to contact them three additional times (one day later, three days later, and one week later). If they cannot be contacted by the third attempt, they will be considered lost to follow-up and will not be contacted again.
13. After the participant completes the study, a retrospective chart review will be conducted to obtain viral load measurements (minimum of 2) from the participant during the time period beginning 3 months prior to their entry into the study and up to 6 months after their entry into the study.

3b. Waitlist-control group

1. After randomization and enrollment, the participant will complete the baseline assessment either at the time of enrollment, at home, or during a subsequent appointment within the next 30 days
2. The interventionist will call the participant after enrollment and do the following:
 - a. Introduce themselves to the patient
 - b. Describe the study timeline
 - c. Discuss follow-up contact times and encourage the participant to stay in contact
 - d. Remind participant of incentives they will receive for participating
 - e. Provide information about the baseline assessment (if the participant has not already completed it)
3. The interventionist will contact participants using their chosen method of communication after 4 weeks to maintain contact and ensure that no adverse events have occurred
4. At 7 weeks, the interventionist will contact participants to obtain their availability for the next week to schedule the first intervention content session based on the shared calendar
5. One day before the videoconferencing session, the researcher will contact the participant via the participant's chosen method of contact to remind them of their appointment
6. At 8 weeks, the patient will come into the clinic to begin the intervention.
7. The patient will be given a laptop to complete the initial assessment battery
8. If the participant is in need of a study phone, the VA coordinator will provide this phone, along with the breathalyzer, to the participant
9. The participant will begin the first intervention session, which will consist of the following content/tasks:
 - a. Introductions and orientation to the technology (smartphone and breathalyzer, stored at the clinic; tutorial handouts provided)

- b. Review of self-monitoring procedures and setting of “do not disturb” hours
 - c. Review of breathing awareness exercise

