In the event that identifying information is released to an unauthorized party, the serostatus of participants could be revealed to unwanted individuals. This could potentially cause harm, but is unlikely considering the careful plans in place regarding data management and protection. All possible measures will be taken to protect information provided through surveys, interviews, and intervention participation, and confidentiality will be respected. Following completion of data collection, responses will become anonymous as identifying information is permanently deleted. For these reasons, we estimate that this minimally-invasive project poses minimal risk.

STATISTICAL ANALYSIS PLAN

For the randomized controlled trial, data analytic methods will be focused on examining acceptability and feasibility, as well as effects on alcohol intake, HAART adherence, and HIV-related medical outcomes (CD4 count and viral load). Intervention adherence, daily monitoring adherence, and session acceptability will be described using descriptive statistics. Session attitudes will be assessed using several 5-point semantic differential attitudinal measures rating the session, including Boring/Interesting, Unpleasant/Pleasant, Bad/Good, Useless/Useful, and Negative/Positive. Scores on the session attitude semantic differential measures will be reverse-coded where required and averaged to form an overall attitude score, with “0” being “neutral.”

We will provide descriptive summaries for the outcome variables, including mean, median, and standard deviation for continuous variables and counts and percentages for categorical variables. We will summarize the outcome variables overall and across the intervention groups. In assessing the differences in alcohol use and medication adherence between the two groups during the 8-week intervention period, we will utilize the Kruskal–Walli’s test, a non-parametric statistical approach, to compare the distribution of outcome variables. The general linear model (ANOVA) will be used to estimate the difference between alcohol use and medication adherence among the groups, and the estimation of the effect size (Cohen’s D) at the end of the 8-week intervention period. While this study was not powered to detect significant differences, the goal of these analyses is to observe changes and effect sizes that may provide preliminary evidence of efficacy.

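### CD4 count is a named outcome, but no planned data source supplies it: every chart-review description is limited to viral load

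*Combined protocol and SAP*

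**What the plan says.** Section 2 (Hypothesis/ General Research Questions) closes with a fifth question: "Does participation in the TRAC intervention impact other clinical HIV outcomes, including CD4 count and viral load". The first paragraph of the SAP repeats the pair as "HIV-related medical outcomes (CD4 count and viral load".

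Section 5 (Data, Collection and record keeping) says that outcomes will be studied by the methods it then lists. The only laboratory entry is: "Retrospective chart review of viral load based on blood draws conducted as part of routine clinical care". The operational steps match it. Step 3a item 13 (intervention group) and Step 3b item 16 (waitlist-control group) both say that "a retrospective chart review will be conducted to obtain viral load measurements (minimum of 2) from the participant". The intervention group's window runs from 3 months before study entry to 6 months after; the waitlist group's runs from 1 month before to 8 months after.

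Section 3 (Study Objectives) is more general. It commits only to "Evaluation of effects on overall alcohol consumption, HAART adherence, and clinical outcomes" and does not name CD4.

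**The concern.** An outcome named in both a research question and the SAP should have a stated source, a time window and a rule for selecting values. Viral load has a source, a window for each group and a minimum of two measurements. CD4 has none of these. A coordinator who carried out the chart review exactly as described would extract no CD4 results, and the analyst would have nothing to summarise or model.

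Timing also matters. Section 5 (Data security Plan) and section 6 say that identifying information is permanently removed once data collection is complete. If the gap is noticed only at analysis, linking CD4 results back to participants may no longer be possible.

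**Working it through.** The plan gives no figure to reproduce, so the check sets the demand for CD4 beside the planned supply.

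**Where CD4 is asked for.** Two places: the fifth research question and the first paragraph of the SAP.

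**Which analyses would use it.** The SAP's descriptive summaries cover the outcome variables generally. Its pooled model is fitted to change from baseline for every outcome, which would need CD4 before and after the intervention. The Kruskal–Wallis and ANOVA/Cohen's d comparisons name only alcohol use and medication adherence. The McNemar tests cover daily alcohol use, breathalyzer results and medication use. So CD4 enters two analyses, neither of them a randomised comparison test.

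**What each source supplies.**

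| Source | Where described | Laboratory marker named | CD4 named? |
|---|---|---|---|
| Chart review, intervention group | Step 3a item 13 | Viral load, at least 2 | No |
| Chart review, waitlist group | Step 3b item 16 | Viral load, at least 2 | No |
| Chart review, list of methods | Section 5 | Viral load | No |
| Assessment battery (baseline, 8, 16, 24 weeks) | Section 5 | None | No |
| Twice-daily surveys and breathalyzer | Section 5 | None | No |
| Post-session questionnaires | Section 5 | None | No |
| Checks before starting | Subject Exclusion Criteria; Step 2 item 5 | Viral load | No |
| Database pull | Section 4, patient selection | None | No |

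The tally is 0 of 3 chart-review descriptions and 0 of 3 questionnaire lists.

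The last two rows are not outcome collection. The checks concern "participants who have not had their viral load tested within the 3 months prior to beginning the intervention" and decide when a participant may begin. The database pull is the one open-ended source: "Clinical data of interest including alcohol dependency diagnoses and prescription use will be pulled from CDW via VINCI, CCR and HAVACS". It is used to build the list of patients to screen, and Step 1 item 10 says that nothing collected in screening becomes study data.

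**Whether the existing windows could serve for CD4.** Counted from study entry they differ: −3 to +6 months (intervention) and −1 to +8 months (waitlist). The waitlist group starts the intervention at week 8, about 2 months after entry. Counted from intervention start, its window is −1 − 2 = −3 to 8 − 2 = +6 months. Taking the intervention group to start at entry, its window is also −3 to +6. The intervention lasts 8 weeks, about 2 months, which leaves about 6 − 2 = 4 months after it ends in each group.

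The windows therefore suit a pooled before/after description. They do not define a common window for a randomised comparison: counted from entry, the period before the intervention is −3 to 0 months in one group and −1 to +2 months in the other.

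**The case against.** The strongest reply is that this is a small wording gap in a pilot that the SAP says was not powered to detect significant differences. The chart review is retrospective and uses routine-care results, so omitting a field is not like omitting a blood draw; CD4 may already be in the same records. No feasibility, alcohol or adherence result depends on it. All of that stands, and it limits the size of the point. It does not remove it: the pilot's stated purpose is to observe changes and effect sizes, and an outcome that nobody is told to extract yields neither.

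Four stronger readings are tempting, and the documents do not support them:

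- *A study objective fails.* Section 3 speaks only of clinical outcomes, which viral load can satisfy. What is affected is part of a research question.
- *CD4 data are lost, or the question can never be answered.* The documents do not say whether or how often CD4 was measured in routine care. What is missing is a planned source.
- *Every data-collection step names viral load alone.* The questionnaires and surveys name neither marker. It is the chart-review descriptions that are confined to viral load.
- *A later, unplanned CD4 extraction would differ between groups.* It might, since no rule is set, but nothing in the documents shows that it would.

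It is also fair to say that adding the field alone would not be enough. Routine draws do not fall at fixed 8- and 16-week points, so a selection rule is needed too.

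**Conclusion.** The inconsistency is real and should be corrected. CD4 is named twice as an outcome and has no planned source. Followed as written, the plan provides no CD4 values for the descriptive summaries or the pooled change-from-baseline model. One of the two named HIV laboratory outcomes, and so half of one of five research questions, would go unanswered. The remaining aims are intact.

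This rests on the data-collection text in sections 4 and 5 being complete. The consent and HIPAA forms and the timeline flowchart were not available to me. No assumption is made about how many participants have CD4 results on record.

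**What to change.** Either of two changes closes the gap.

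**Collect it.** In Step 3a item 13, Step 3b item 16 and the section 5 list of methods, extend the chart review to all viral load and CD4 results with their collection dates, using results already in the record and each group's existing window. In the SAP:

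- take the last CD4 result before intervention start as the pre value and the first after intervention end as the post value;
- report how many participants have both;
- state that CD4 is descriptive and belongs to the pooled before/after analysis only, with no between-group claim.

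Do this before identifiers are deleted.

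**Or drop it.** Remove CD4 from the fifth research question and from the first paragraph of the SAP, so that no CD4 conclusion is expected.

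The first option costs one more field in a review already planned, with no added visit or blood draw. Its drawbacks are incomplete coverage, because routine care may not supply a value on both sides of the intervention for everyone, and possibly a check that the HIPAA authorization covers CD4. The second is a text edit that gives up the CD4 question.
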